#### 4.16 Data Presentation

Data will be presented in the form of table and graphs. Descriptive statistics will be presented with frequency table. Association will be illustrated with cross tables and test statistics will be added in the foot note of the table. Bar and pie charts will be generated to illustrate descriptive statistics.

#### 5 **Ethical considerations**

#### Approval has already been taken from

National Research Ethics Committee,

Bangladesh Medical Research Council (BMRC)

[contact] Email: [contact]

[name], Bangladesh.

Approval Number: 076 (1) 25 10 2017

Informed written consent (Annexure - ) will be taken from the participant after explaining all the facts, potential dangers to the subjects in case of primary data collection. The study involves collection of non-sensitive Socio-demographic data (primary data), compilation of hospital and treatment records (secondary data) to be conducted researcher under supervision of relevant specialists along with few diagnostic test. The participants will be assured that the information acquired will be used for academic purpose. They will be assured of confidentiality, and for the purpose of data analysis no individual data were reported rather de identified data will be preceded for analysis.

#### 6 Resources

#### **6.1 Space and Budget**

- **a)** Principal and other investigators have their respective offices in the premises of the Bangladesh Laser & Cell Surgery Institute & Hospital, Dhaka, Bangladesh.
- **b)** "Bangladesh Laser & Cell Surgery Institute & Hospital" Dhaka, Bangladesh has adequate facilities to carry out the procedure in its operation theater.
- c) "Bangladesh Laser & Cell Surgery Institute & Hospital" Dhaka, Bangladesh has adequate facility to carry out post-operative management of the subjects of the current study.

24

- d) "Bangladesh Laser & Cell Surgery Institute & Hospital" Dhaka, Bangladesh has proposed the budget for their operative and post- operative cost and the cost of the hospital stay.
- e) "Bangladesh Laser & Cell Surgery Institute & Hospital, Dhaka, Bangladesh". has proposed the budget for data collection, data processing and rounding up the study over the expected time period.

#### **6.2 Facilities**

- (a) Lab facilities (all modern equipments and Lab materials are available)
- (b) Man power facilities (mentioned investigators, Co- investigators, Anesthesiologist, Medical Officer, Nurse, Ward Boy)

#### 6.3 Materials

- **a) Study population** According to sample size calculation 31 patients with established CKD will be recruited in the study over the estimated study period.
- **b) Equipment** "UNISTATIONTM" a specially designed medical device to satisfy diverse demands for various autologous cell therapies.

UNISTATION is a specially designed medical device to satisfy diverse demands for various autologous cell therapies with only one device. PRP, PRF isolation, and fat purification functions have been added to UNISTATIONTM.

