4.1 Study design

Study Type: Interventional.

Primary Purpose: Treatment

Study Phase: Phase 1/Phase 2

Interventional Study Model: Parallel Assignment

Participants will be placed in either of the 2 groups, depending on

the number of harvested total stem cell count.

Those having a harvested total "Adipose Derived Stem Cell

(ADSC)" count (in 5 ml SVF solution) between 1 x 10^6 to 2 x

10^6 will be placed in "Group A".

13

Those having a harvested total "Adipose Derived Stem Cell (ADSC)" count (in 5 ml SVF solution) more than 2 x 10^6 will be placed in "Group B".

Both groups will be studied for Phase I/ Phase II trial by the proposed outcome measures over the stipulated time frame.

Those having a harvested total "Adipose Derived Stem Cell (ADSC)" count (in 5 ml SVF solution) less than 1 x 10^6 will be excluded from the study.

Number of Arms: 2

Masking: Triple (Participant, Care Provider, Outcomes Assessor)

Allocation: Non-Randomized

Enrollment: 31 [Anticipated]

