#### 4.6 Sample size determination:

 $\alpha$  (two-tailed) = Threshold probability for rejecting the null hypothesis. Type I error rate.

 $\beta$  = Probability of failing to reject the null hypothesis under the alternative hypothesis. Type II error rate.

E = Effect size

 $S(\Delta)$  = Standard Deviation of the change in the outcome.

Here,  $\alpha = 0.05$ 

 $\beta = 0.20$ 

E = 0.5

 $S(\Delta) = 1.0$ 

The standard normal deviate for  $\alpha = Z_{\alpha} = 1.960$ 

The standard normal deviate for  $\beta = Z_{\beta} = 0.842$ 

A = 1.000

$$B = (Z_{\alpha} + Z_{\beta})^2 = 7.849$$

$$C = (E/S(\Delta))^2 = 0.250$$

Sample size N = AB/C = 31 (approx.)

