#### 4.8.2 Exclusion criteria

Any patient meeting any of the exclusion criteria will be excluded from study participation.

- 1) Known hypersensitivity to any component used in the study.
- 2) With inadequate hematologic function with: absolute neutrophil count (ANC) <1,500/μL OR platelets < 100,000/μL OR Hemoglobin < 8 g/dL
- 3) With impaired hepatic function with: serum bilirubin, aspartate aminotransferase (AST), alanine aminotransferase (ALT) or alkaline phosphatase (AKP), prothrombin time above and normal reference and serum albumin below normal reference range.
- 4) With hemoglobin A1c (HbA1c) > 8.0%
- 5) With serious prior or ongoing medical conditions (e.g. concomitant illness such as cardiovascular (e.g. New York Heart Association grade III or IV), hepatic e.g. Child-Pugh Class C), psychiatric condition, alcoholism, drug abuse), medical history, physical findings, ECG findings, or laboratory abnormality that in the investigators' opinion could interfere with the results of the trial or adversely effect the safety of the patient

- 6) Pregnant or lactating women or premenopausal with childbearing potential but not taking reliable contraceptive method(s) during the study period
- 7) With known history of human immunodeficiency virus (HIV) infection or any type of hepatitis
- 8) Judged to be not applicable to this study by investigator such as difficulty of followup observation
- 9) With any other serious diseases/medical history considered by the investigator not in the condition to enter the trial
- 10) Known or suspected abuse of alcohol or narcotics
- 11) With known history of cancer within past 5 years
- 12) With any autoimmune disease
- 13) With congenital kidney disease
- 14) With precancerous condition or with raised tumour markers like Alpha feto protein, Carcino embryonic antigen (CEA), C.A 19.9, C.A 125, Serum PSA above normal reference range.
- 15) Participants having a harvested total "Adipose Derived Stem Cell (ADSC)" count (in 5 ml SVF solution) less than 1 x 10^6 will be excluded from the study.

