#### Serious adverse events (SAEs)

- i) Anaphylaxis (Immediate)
- ii) Pulmonary embolism or infarction (Immediate)
- iii) Outset of any neoplastic change (Late)
- iv) Outset of new Cardiovascular events (Late)
- v) Outset of new Cerebrovascular or neurological events (Late)
- vi) Reactivation of treated tuberculosis (Late)
- b) Change from baseline to 24 week visit in estimated glomerular filtration rate (eGFR) and split renal function in all patients for Phase II [Time Frame: Weeks 0, 24]
  - eGFR with split renal function will be evaluated using DTPA Renogram.
- c) Change from baseline to 24 week visit in estimated glomerular filtration rate (eGFR) with serum creatinine level in patients with CKD 4 and below for Phase II [Time Frame: Weeks 0, 2, 4, 12, 24]
  - eGFR will be calculated by Serum Creatinine level using MRDR formula during all visits.
- d) Change from baseline to 24 week visit in need for dialysis in patients with CKD 5 for phase II [Time Frame: Weeks 0, 2, 4, 12, 24]

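### The 31 in section 4.6 counts analysable before-after changes, but 4.1 and 6.3 use it as the number enrolled, with no allowance for loss and no stated replacement rule

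*Combined protocol and SAP*

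**What the plan says.** Section 4.6 sets a two-sided alpha of 0.05, beta 0.20, an effect of 0.5 and a spread of 1.0, the latter defined as the "Standard Deviation of the change in the outcome". It uses a factor A of 1.000 and ends with "Sample size N = AB/C = 31 (approx". No step follows that figure, and the section names no outcome, unit or visit.

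The same number then appears in two other places. Section 4.1 has "Enrollment: 31 [Anticipated". Section 6.3 has "According to sample size calculation 31 patients with established CKD will be recruited in the study over the estimated study period".

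Three other parts of the protocol bear on how many of the 31 reach the analysis:

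- Exclusion criterion 15 in 4.8.2 (also in 4.1) states that participants whose harvested cell count is below 1 x 10^6 "will be excluded from the study". By section 7, that count exists only after liposuction and processing.
- Primary outcome (b) in 4.11.1 is the "Change from baseline to 24 week visit in estimated glomerular filtration rate (eGFR) and split renal function in all patients", which needs a renogram at weeks 0 and 24.
- Section 4.7 keeps recruitment open until the wanted sample is reached. Section 4.3 runs the study until the sample requirement is complete, with at least a year of follow-up. Neither says which patients count towards the sample, or whether an excluded or lost patient is replaced.

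Section 4.15 gives no method for a patient without a follow-up value.

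**The concern.** A formula built on the standard deviation of a change counts changes, and a patient supplies one only with both a baseline and a follow-up measurement. Enrolment is a different and normally larger number. Using one figure for both amounts to planning for no loss between recruitment and week 24. The population has CKD stage 3 to 5, an eGFR down to 0 and ages up to 80, and the protocol neither states nor defends that assumption.

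What is at stake is the meaning of a non-significant result. A reader will set it against the stated 80% power. If fewer than 31 patients contribute a change, the study's real sensitivity is lower than that, and the plan gives no figure for how much lower.

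**Working it through.** **Inputs from 4.6.** Z for alpha = 1.960; Z for beta = 0.842; E = 0.5; SD of the change = 1.0; A = 1.000.

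**The plan's own figure.** N = A(Zα + Zβ)²/(E/SD)² = 7.849/0.25 = 31.4, stated as 31. It reproduces. Other designs with the same inputs do not give 31: a one-sided test gives 24.7, and a two-group comparison gives 63 per group. So 31 is a one-sample, before-after count. Rounding up would give 32.

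**Power with no loss.**
- Normal formula: Φ(0.5√n − 1.960). At n = 31 this is Φ(2.784 − 1.960) = Φ(0.824) = 79.5%, so beta is 0.205.
- Paired t (noncentral t, n − 1 degrees of freedom, noncentrality 0.5√n): 76.8% at n = 31. It first exceeds 80% at n = 34 (80.8%); n = 33 gives 79.5%.
- One lost pair (n = 30): 78.2% by the normal formula, 75.4% by paired t. There is no margin, because 31.4 was already rounded down.

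**Power under loss.** The documents give no loss rate; these rates are assumptions. Pairs are 31 × (1 − loss), to the nearest patient.

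| Assumed unreplaced loss | Pairs | Power, paired t | Power, normal formula |
|---|---|---|---|
| 0% | 31 | 77% | 80% (79.5%) |
| 5% | 29 (29.45) | 74% | 77% |
| 10% | 28 (27.9) | 72% | 75% |
| 15% | 26 (26.35) | 69% | 72% |
| 20% | 25 (24.8) | 67% | 71% |

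If the 31 were also counted before harvest, and 10% failed the cell count and 10% of the rest were lost, then 31 × 0.9 × 0.9 = 25.1. That is 25 pairs, the same as the 20% row.

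**Effect detectable with 80% power, paired t.** 0.52 SD with 31 pairs, 0.55 SD with 28, 0.58 SD with 25. By the normal formula, 2.802/√n gives 0.50, 0.53 and 0.56 SD.

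**The case against.** The strongest reply is that the text can be read as already protecting the 31. The low cell count is an eligibility criterion, 4.7 recruits by the eligibility criteria until the sample is reached, and 4.3 ties completion to the sample requirement with a year of follow-up. On that reading, 31 qualifying patients, perhaps even 31 followed patients, are intended. This stands in part. A reader might infer that the 31 is definitely counted before the post-harvest exclusion, but the documents do not settle that. They do not settle the opposite either, because the word sample is left undefined and no replacement rule is given.

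A second reply is that the sponsor's arithmetic is sound. With 31 complete pairs its own formula gives 79.5%, which agrees with beta 0.20 after rounding. That stands. A reader might infer that the stated power is missed outright, for every outcome. The documents do not support this: by the plan's formula the shortfall depends on unreplaced loss, at rates the plan does not give. The paired t figures add a small-sample correction that is separate from attrition, and 4.15 does not commit to a t-test.

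Third, 4.6 names no outcome, so applying it to outcome (b) at week 24 is an inference. It is a generous one, since (b) is the only Phase II primary outcome that covers all patients; (c) and (d) use subsets.

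Finally, a few points of power matter less in a non-randomised Phase 1/2 study with an anticipated enrolment. That bears on how much weight the point carries. It does not remove the need to say what the 31 counts.

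**Conclusion.** The point holds in conditional form. The calculation in 4.6 is correct for what it computes, but its result is a number of analysable changes, and 4.1 and 6.3 carry it unchanged as enrolment and recruitment. The stated beta of 0.20 is met only with 31 complete pairs, and then only by the normal formula. Any unreplaced loss lowers the power, even for the all-patient outcome (b).

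For assumed losses of 5% to 20%, the shortfall against 80% is about 3 to 9 points by the normal formula and about 6 to 13 points by paired t; about 3 points of the latter are present with no loss at all. These sizes rest on the assumed loss rates, on lost patients not being replaced, and on linking 4.6 to outcome (b). This is a missing allowance and an undefined count. It is not a calculation error.

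**What to change.** 1. In 4.1 and 6.3, state that 31 means patients infused, and in 4.7 say explicitly that patients excluded for a low count are replaced. If 31 was meant as patients recruited before harvest, this adds a few harvests and infusions. In that case the sponsor may instead keep 31 recruited and restate the power at the smaller number.
2. In 4.3 or 4.7, say whether patients lost after infusion are replaced.
3. In 4.6, name the outcome and visit to which the calculation applies, and give the power at the expected evaluable number, with the loss rate labelled as an assumption. Possible wording: *Assuming about 10% loss, 28 of 31 patients are expected to be evaluable; power for a change of 0.5 SD is then about 72% by paired t-test (75% by the normal formula), and 80% power holds for about 0.55 SD (paired t).*

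The cost is a less favourable stated power. Apart from the possible extra harvests and infusions in step 1, and any replacement of lost patients that the sponsor chooses under step 2, the change is one of wording.

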#### 7 **Procedure**

After harvesting the abdominal adipose tissue via liposuction SVF (stromal vascular fluid) are collected. Subsequently these are centrifuged in UNISTATIONTM, a centrifuge machine specifically manufactured for this purpose. Later it is mixed with collagenase solution and fat is separated. Stem cells containing SVF is collected after centrifugation. SVF is neutralized and washed with normal saline. Then it is washed with patient's own serum and normal saline. A sample is collected for cell counting by **Luna automated cell counter**. The final SVF is ready for subcutaneous or IV injection if 80-90% of cell remain viable, active and mobile.

As it is a closed door automatic procedure within a same machine, so after collection of 40ml of sub-cutaneous fat, all procedures are automated. So there is no chance of contamination. Steps are mentioned below.

#### 1st Step: Fat washing(A1):

- (1) To aspirate 40 ml fat and to take 40 ml water for balance in 2 UNIKITs.
- (2) To put them is UNISTATIONTM Centrifuge.
- (3) To touch SVF button once (Display shows A1)
- (4) To touch start button once A1 is shown.
- (5) After centrifugation, to remove RBC layer from the bottom.
- (6) To collect 20ml pure fat after removing RBC layer in another UNIKIT.

# 2nd Step: Collagenase Digestion(A2):

- (1) To prepare 20ml of 0.1% collagenase Solution.
- (2) To transfer the Collagenase solution in to the pure fat.
- (3) To place shaking plate and put the pure fat with collagenase on if and close the door
- (4) To touch SVF button once again (Display shows A2)
- (5) To touch Start button once A2 is shown.
- (6) To wait for 30 min for shaking incubation and take the fat out after finishing shaking incubation.

# 3rd Step: SVF Collection(A3):

- (1) To put the collagen digested fat in UNISATION  $^{\text{TM}}$  Centrifuge.
- (2) To touch SVF button once again (Display shows A3)
- (3) To touch Start button once A3 is shown.
- (4) After centrifugation, to take out UNIKIT very slowly so that layers should not be mixed. (Stem cell are at the bottom in 5ml SVF)
- (5) Before removing cap to put the hand piece upwards so that stem cells should not be kept in the cap.

(6) To transfer 5ml SVF at the bottom into a 5ml or 10ml syringe and transfer it again into another UNIKIT.

# 4th Step: Neutralization and Washing of SVF(A4):

- (1) To transfer 5ml PPP into the 5ml SVF.
- (2) To transfer 30ml Normal saline into the 10ml of SVF and PPP.
- (3) To put it in  $UNISTATION^{TM}$  Centrifuge.
- (4) To touch SVF button once again (Display shows A4)
- (5) To touch Start button if A4 is shown.
- (6) After centrifugation. To transfer 5ml SVF at the bottom into 5ml or 10ml syringe.

## **Final Step: Preparation for Injection**

To transfuse the final 5 ml of SVF to the patient through intravenous route. Before that to collect few drops of SVF sample for cell counting by Luna Stem automated fluorescent cell counter.

#### **ANNEXURE - C**

#### **QUESTIONNAIRE - 1**

#### (CLINICAL ASSESSMENT - DURING ALL VISITS)

**PARTICULARS OF THE PATIENT: CODE NO:** NAME: AGE: SEX: M/F**HOSPITAL REG. NO:** PHONE: **ADDRESS: CONTACT PERSON:** PHONE: **DIAGNOSIS (Put Tick Mark Beside The Appropriate Selection):** 1) CKD: Stage 3A Stage 3B Stage 4 Stage 5 a) GN Need for dialysis Score b) IgA Nephropathy a) No dialysis yet 0 1 c) FSGS b) Occasional (> 6 days interval) d) Interstitial Nephritis c) At 6 (six) days interval / Once weekly 2 3 e) No Biopsy done d) At 5 (five) days interval e) At 4 (four) days interval 4 f) At 3 (three) days interval / 2 times a week 5 6 g) At 2 (two) days interval 7 h) At 1 (one) day interval / 3 times a week -2) HYPERTENSION 3) DM 4) Hypothyroidism 5) HYPERPARATHYROIDISM 6) IHD < NyHA Gr III or IV 7) CLD < Child Pugh C 8) CVD 9) OTHERS (if any) **SYMPTOMS (Put Tick Mark Beside The Appropriate Selection):** Better/Good/As usual/Bad/Worse **Urine output:** Scanty / Reduced / Normal **General Welbeing** Anorexia: Yes / No Convulsion: Yes / No Yes / No Loss of Consciousness: Yes / No Nausea: Vomiting: Yes / No Muscle spasm: Yes / No Hiccough: Yes / No Pain Yes / No Weakness: Yes / No **Fever** Yes / No Weight loss: Yes / No Yes / No Headache: Swelling of body: Yes / No **Respiratory distress:** Yes / No Vertigo: Yes / No Chest pain: Yes / No Constipation: Yes / No **Abdominal Pain:** Yes / No Loose motion: Yes / No Others (if any): **SIGNS: Body weight: Blood pressure:** Oedema:

35

**Dehydration:** 

**Respiration:** 

Pulse:

Temperature: Others (if any):

# ANNEXURE - C

#### **QUESTIONNAIRE - 2**

(CONCOMITANT TREATMENT - DURING ALL VISITS)

PARTICULARS OF THE PATI	ENT:		CODE	NO:	
NAME:		AGE:		SEX:	
REG. NO:					
TYPE OF MEDICINE	NAME OF MEDICINE		DOSE		CHANGES IF ANY
ANTIHYPERTENSIVE					
HYPOGLYCAEMIC					
ANTIBIOTICS					
ANALGESICS					
ANTIULCERANT					
VITAMINS & MINERALS					
OTHERS					

#### **ANNEXURE - D**

(INVESTIGATIONS - 1ST VISIT - 0 WEEK)

**PARTICULARS OF THE PATIENT: CODE NO:** 

AGE: NAME: SEX: M/F

**REG. NO:** 

**INVESTIGATIONS for Fitness & Maintainence: INVESTIGATIONS for Outcome Measures:** 

**DTPA Renogram Total GFR** S.URIC ACID Right

Left

CBC/ESR

Hb (gm/dl) ESR (mm in 1st hour)

PLATELET COUNT (K/ul)

**WBC** 

Neutrophil (%) Lymphocyte (%) Monocyte (%)

Eosinophil (%) Basophil (%)

**BIOCHEMICAL:** 

**RBS** HbA1C

S. Creatinine

e GFR (ml/min/1.73 m^2)

**BUN** 

**Urine Microalbumin-Creatinine Ratio (UMCR) Urinary Total Protein-Creatinine ratio(UPCR)** 

**TUMOUR MARKERS** 

S. ALPHA FETO PROTEIN

S. CEA S. C.A 19.9 S. CA 125

S. Beta 2 Microglobulin

S. LDH

S. PSA

**BIOCHEMICAL:** 

S. Vit D3

S. Calcium

S. Phosphate

S. ELECTROLYTES:

**SODIUM** 

**POTASSIUM** 

**CHLORIDE** 

TCO2

**ANION GAP** 

**HORMONES** 

S. PTH

S. TSH

FT4

**LIVER PROFILE** 

**HBsAg** 

**Anti HCV** 

ALT

S. Albumin

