#### 2.8 Route of delivery

Various routes for delivery of ADSCs, ADSC-induced cells, or ADSCs combined with compound materials have been developed for the treatment of different diseases or damaged tissue. These routes can be classified into two categories: systemic delivery through blood vessels (intravenous injection or intra-arterial injection) or local delivery directly into injured tissues or organs [32].

The route of MSC delivery may influence the cells' capacity to home and engraft the damaged tissue, and thereby their efficacy for renal repair. Commonly used experimental methods to deliver MSCs include systemic intravenous, intra-arterial, or intra-parenchymal delivery. In nonhuman primates the cells distribute broadly into the kidneys, skin, lung, thymus, and liver with estimated levels of engraftment ranging from 0.1 to 2.7% [33].

The route of MSC delivery, intravenous, intra-arterial, or intra-parenchymal, may affect their efficiency for kidney repair. When labeled MSC intravenously infused into baboons were observed for 9-21 months, estimated levels of engraftment in the kidney, lung, liver, thymus, and skin ranged from 0.1-2.7% [33] Indeed, the intravenous route lags in delivery efficiency, because MSC may initially be trapped in the lungs[34] Intra-arterial infusion of MSC was the most effective route to achieve immunomodulation in rat kidney transplantation, possibly by avoiding lodging in the pulmonary circulation, allowing MSC to home to the injured kidney [35].

An important feature of MSCs is their capacity to induce proliferation of renal glomerular and tubular cells, increasing cellular survival. By secreting proangiogenic and trophic factors, injected MSCs not only can enhance proliferation, but also can decrease apoptosis of tubular cells [36]. Several routes of administration (intra-parenchymal, sub-capsular, intravenous) have

been explored and all seem to be effective. Multiple, repeated injections of MSCs appear to be even more effective than single injections [37,38].

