**ECG** 

**ECHOCARDIOGRAM** 

**OTHERS (If any)** 

#### **ANNEXURE - D**

#### (INVESTIGATIONS)

(2nd/3rd/4th/6th VISIT - 2/4/12/36 Weeks)

PARTICULARS OF THE PATIENT: CODE NO:

NAME: AGE: SEX: M / F

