**ANION GAP** 

**Urine R/M/E** 

#### **ANNEXURE - D**

(INVESTIGATIONS)

(5th / 7th VISIT - 24, 48 WEEK)

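### Liver function gates entry and is partly tested at week 0, but no follow-up liver test is visible, so symptomless biochemical liver change would not be systematically measured

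*Combined protocol and SAP*

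**What the plan says.** Section 4.8.2, exclusion 3, removes patients on liver tests: "With impaired hepatic function with: serum bilirubin, aspartate aminotransferase (AST), alanine aminotransferase (ALT) or alkaline phosphatase (AKP), prothrombin time", with serum albumin also named. The week-0 form in Annexure D has a block headed "LIVER PROFILE" that lists hepatitis B and C serology, ALT and albumin; prothrombin time follows it.

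Section 4.10 sends all investigations before and after treatment to Annexure D. That annexure has two follow-up forms, "2nd/3rd/4th/6th VISIT - 2/4/12/36 Weeks" and "5th / 7th VISIT - 24, 48 WEEK". Both repeat uric acid, calcium, phosphate and electrolytes. The second adds the renogram, the urinary protein ratio and the tumour markers. Neither shows a liver function test in its readable text.

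Safety is specific objective (i) in section 3.2, and adverse-event incidence to week 48 is primary outcome (a) in section 4.11.1. The lists of minor and serious events there name no hepatic event. None of the primary outcomes or the 20 secondary outcomes, (a) to (t), is a liver function test.

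The product is given intravenously to both groups (section 4.2). Section 2.8 says, of nonhuman primates, that "the cells distribute broadly into the kidneys, skin, lung, thymus, and liver".

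**The concern.** The protocol treats liver function as important enough to bar a patient from entry, and it takes three of the relevant tests at week 0. It then schedules no second measurement that can be seen. Half of a before-and-after comparison is collected and the other half is not.

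At stake is how far the safety conclusion reaches. A change in ALT, albumin or prothrombin time that causes no symptoms would have no planned place in the data. A week-48 statement that the treatment was safe would then be silent on liver biochemistry, and no rate or confidence bound could be given for it.

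**Working it through.** **The plan's own figure.** Section 4.6 uses a two-sided alpha of 0.05, beta 0.20, E = 0.5 and S(Δ) = 1.0. N = (1.960 + 0.842)² / (0.5/1.0)² = 7.85 / 0.25 = 31.4, which agrees with "Sample size N = AB/C = 31 (approx". The point does not depend on this calculation; 31 is used below only as the number of patients.

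**Entry criterion, forms and outcomes side by side.**

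| Test | Exclusion 3 | Week-0 form | Weeks 2/4/12/36 form | Weeks 24/48 form, readable part | Outcome in 4.11 |
|---|---|---|---|---|---|
| ALT | yes | yes | no | no | no |
| Albumin | yes | yes | no | no | no |
| Prothrombin time | yes | yes | no | no | no |
| Bilirubin | yes | no | no | no | no |
| AST | yes | no | no | no | no |
| AKP | yes | no | no | no | no |

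The first three rows show the gap in follow-up. The last three show a separate mismatch: they are entry criteria with no named line on the week-0 form, which has only an open line for other tests.

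**How secure each absence is.** The week 2/4/12/36 form is followed directly by the next form, so its list is complete: four of the six post-treatment visits have no liver test. The readable text of the week 24/48 form stops at the anion gap. On the week-0 form the liver block comes after that line, so for the other two visits the absence is probable but not certain. The outcome list, which does not depend on that page, points the same way.

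**What measuring would give, for scale.** The documents give no rate of liver abnormality, so a range is assumed. With true rate p and 31 patients measured, the chance of at least one abnormality is 1 − (1 − p)³¹:

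- p = 1%: 1 − 0.99³¹ = 26.8%
- p = 2%: 1 − 0.98³¹ = 46.5%
- p = 5%: 1 − 0.95³¹ = 79.6%
- p = 10%: 1 − 0.90³¹ = 96.2%

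If none were seen in 31, the one-sided 95% upper bound is 1 − 0.05^(1/31) = 9.2%; the upper end of the two-sided exact 95% interval is 1 − 0.025^(1/31) = 11.2%. These figures assume that all 31 patients are measured and that p counts only abnormalities present when blood is drawn.

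**Assays.** 3 tests × 31 patients = 93 per added visit. One early visit plus weeks 24 and 48 is 3 × 93 = 279.

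**The case against.** A reader might infer that the trial cannot detect liver harm at all. The documents do not support that. Questionnaire 1 is completed at every visit; it has a chronic liver disease box, asks about anorexia, nausea, vomiting, abdominal pain and swelling, and leaves a free line. AFP, which section 4.11.2 names as a marker of hepatocellular carcinoma, is repeated at weeks 24 and 48. Section 4.12 plans a checklist of hospital records and laboratory reports, so a liver value from routine care might be picked up. None of these is a systematic measurement of liver function.

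A reader might also infer that the protocol expects this product to reach the liver. Section 2.8 is background on infused MSC in nonhuman primates, with engraftment of 0.1 to 2.7% across several organs and some initial trapping in the lungs. It says nothing about non-expanded SVF in patients and reports no hepatic harm. The case for follow-up rests instead on the entry criterion and the safety objective.

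Third, it is tempting to say that no liver value will exist at any of six visits. That is secure for four; the last page must be checked for weeks 24 and 48.

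Two further objections stand as limits. Testing at weeks 24 and 48 alone would miss a transient early rise. And every participant is treated, so an abnormal value could not readily be attributed to the treatment. Neither is a reason to leave the tests out.

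**Conclusion.** The gap is real but limited. Liver function decides entry, three of its tests are taken at week 0, and no liver function test is on the week 2/4/12/36 form, on the readable part of the week 24/48 form, or among the outcomes. Symptomless biochemical change would not be systematically measured, and the safety conclusion could not extend to it.

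The size is best stated as information forgone. Repeat testing of 31 patients would be likely to reveal a fairly common abnormality (80% at an assumed 5%) and would often miss a rare one (27% at 1%). A clean result would still bound the rate at about 9%; with no scheduled test there is no bound. The conclusion for weeks 24 and 48 rests on the original page listing nothing further. Efficacy outcomes and the sample size are unaffected.

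**What to change.** 1. Check the original page of the week 24/48 form for liver tests below the anion gap line.
2. Add ALT, serum albumin and prothrombin time to at least one early visit on the week 2/4/12/36 form, where the gap is certain, and to weeks 24 and 48 if they are not already there.
3. For each test, report the number of patients who move from within the reference range at week 0 to outside it, over those measured, with an exact 95% confidence interval. Present this as a descriptive safety result without causal attribution, since there is no untreated arm.
4. Reconcile exclusion 3 with the week-0 form on bilirubin, AST and AKP, so that the entry criterion and the recorded tests agree.

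The cost is a protocol and form amendment and 93 routine assays per added visit (279 for three), at visits where blood is already drawn. No visit is added. The downside, besides laboratory cost, is that some values will be abnormal by chance and will need explaining.
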